5.0 THERAPEUTIC/DIAGNOSTIC AGENTS

5.1 Lenalidomide

Lenalidomide, a thalidomide analogue, is an immunomodulatory agent with anti-angiogenic properties. The chemical name is 3-(4-amino-1-oxo 1,3-dihydro -2*H*-isoindol-2-yl) piperidine-2,6-dione and it has the following chemical structure:

Chemical Structure of Lenalidomide

3-(4-amino-1-oxo 1,3-dihydro-2*H*-isoindol-2-yl) piperidine-2,6-dione

The empirical formula for lenalidomide is C₁₃H₁₃N₃O₃, and the gram molecular weight is 259.3.

Lenalidomide is off-white to pale-yellow solid powder. It is soluble in organic solvent/water mixtures, and buffered aqueous solvents. Lenalidomide is more soluble in organic solvents and low pH solutions. Solubility was significantly lower in less acidic buffers, ranging from about 0.4 to 0.5 mg/ml. Lenalidomide has an asymmetric carbon atom and can exist as the optically active forms S(-) and R(+), and is produced as a racemic mixture with a net optical rotation of zero.

5.1.1 Clinical Pharmacology

Mechanism of Action:

The mechanism of action of lenalidomide remains to be fully characterized. Lenalidomide possesses immunomodulatory and antiangiogenic properties. Lenalidomide inhibited the secretion of pro-inflammatory cytokines and increased the secretion of anti-inflammatory cytokines from peripheral blood mononuclear cells. Lenalidomide inhibited cell proliferation with varying effectiveness (IC50s) in some but not all cell lines. Of cell lines tested, lenalidomide was effective in inhibiting growth of Namalwa cells (a human B cell lymphoma cell line with a deletion of one chromosome 5) but was much less effective in inhibiting growth of KG-1 cells (human myeloblastic cell line, also with a deletion of one chromosome 5) and other cell lines without chromosome 5 deletions. Lenalidomide inhibited the expression of cyclooxygenase-2 (COX-2) but not COX-1 in vitro.

Pharmacokinetics and Drug Metabolism:

Absorption:

Lenalidomide, in healthy volunteers, is rapidly absorbed following oral administration with maximum plasma concentrations occurring between 0.625 and 1.5 hours post-dose. Co-administration with food does not alter the extent of absorption (AUC) but does reduce the maximal plasma concentration (C_{max}) by 36%. The pharmacokinetic disposition of lenalidomide is linear. C_{max} and AUC increase proportionately with increases in dose. Multiple dosing at the recommended dose-regimen does not result in drug accumulation.

Pharmacokinetic analyses were performed on 15 multiple myeloma patients treated in the phase I studies. Absorption was found to be rapid on both Day 1 and Day 28 with time to maximum blood levels ranging from 0.7 to 2.0 hours at all dose levels (5mg, 10mg, 25mg, and 50mg). No plasma accumulation was observed with multiple daily dosing. Plasma lenalidomide declined in a monophasic manner with elimination half-life ranging from 2.8 to 6.1 hours on both Day 1 and 28 at all 4 doses. Peak and overall plasma concentrations were dose proportional over the dosing range of 5mg to 50mg. Exposure (AUC) in multiple myeloma patients is 57% higher than in healthy male volunteers.

Pharmacokinetic Parameters:

Distribution:

In vitro (¹⁴C)-lenalidomide binding to plasma proteins is approximately 30%.

Metabolism and Excretion:

The metabolic profile of lenalidomide in humans has not been studied. In healthy volunteers, approximately two-thirds of lenalidomide is eliminated unchanged through urinary excretion. The process exceeds the glomerular filtration rate and therefore is partially or entirely active. Half-life of elimination is approximately 3 hours.

MEMORIAL SLOAN-KETTERING CANCER CENTER
IRB PROTOCOL

IRB#: 11-107A(12)

5.1.2 Supplier(s)

Celgene Corporation will supply Revlimid® (lenalidomide) to study participants at no charge through Celgene's Revlimid Risk Evaluation and Mitigation Strategy™ (REMS) (formerly known as RevAssist® Program).

5.1.3 Dosage form

Lenalidomide will be supplied as capsules for oral administration.

5.1.4 Packaging

Lenalidomide will be shipped directly to patients. Bottles will contain a sufficient number of capsules for one cycle of dosing.

5.1.5 Storage

Lenalidomide should be stored at room temperature away from direct sunlight and protected from excessive heat and cold.

5.1.6 Prescribing Information

Lenalidomide (Revlimid®) will be provided to research subjects for the duration of their participation in this trial at no charge to them or their insurance providers. Lenalidomide will be provided in accordance with the Celgene Corporation's Revlimid REMS® program. Per standard Revlimid REMS® program requirements, all physicians who prescribe lenalidomide for research subjects enrolled into this trial, and all research subjects enrolled into this trial, must be registered in, and must comply with, all requirements of the Revlimid REMS® program.

Only enough lenalidomide for one cycle of therapy will be supplied to the patient each cycle.

5.1.7 Pregnancy Testing

Pregnancy tests for females of childbearing potential. A female of childbearing potential (FCBP) is a sexually mature female who: 1) has not undergone a hysterectomy or bilateral oophorectomy; or 2) has not been naturally postmenopausal for at least 24 consecutive months (i.e., has had menses at any time in the preceding 24 consecutive months).

Pregnancy tests must occur within 10 – 14 days and again within 24 hours prior to prescribing lenalidomide for Cycle 1 (prescriptions must be filled within 7 days). FCBP with regular or no menstruation must have a pregnancy test weekly for the first 28 days and then every 28 days while on therapy (including breaks in therapy); at discontinuation of lenalidomide and at Day 28 post the last dose of lenalidomide. Females with irregular menstruation must have a pregnancy test weekly for the first 28 days and then every 14 days while on therapy (including breaks in therapy), at discontinuation of lenalidomide and at Day 14 and Day 28 post the last dose of

MEMORIAL SLOAN-KETTERING CANCER CENTER IRB PROTOCOL

IRB#: 11-107A(12)

[figure not shown]
lenalidomide (see Appendix: Risks of Fetal Exposure, Pregnancy Testing Guidelines and Acceptable Birth Control Methods).

5.2 Dexamethasone

5.2.1 Description

Dexamethasone is a synthetic adrenocortical steroid. Corticosteroids are naturally-occurring chemicals produced by the adrenal glands located above the kidneys. Corticosteroids affect the function of many cells within the body and suppress the immune system. Corticosteroids also block inflammation and are used in a wide variety of inflammatory diseases affecting many organs.

The molecular weight for dexamethasone is 392.47. It is designated chemically as 9-fluoro-11 β ,17,21-trihydroxy-16 α -methylpregna-1,4-diene-3,20-dione. The empirical formula is C₂₂H₂₉FO₅ and the structural formula is:

Dexamethasone is stable in air and almost insoluble in water.

5.2.2 Form

Dexamethasone is a white to practically white, odorless, crystalline powder. It is available in 2 or 4 mg tablets (commercially) for oral administration. Each tablet contains dexamethasone as the active ingredient, and the following inactive ingredients: calcium phosphate, lactose, magnesium stearate, and starch. The tablet shell may contain the following: D&C Yellow 10, FD&C Yellow 6, and/or FD&C Blue 1.

5.2.3 Storage and Stability

All investigational study drugs will be stored in a locked, safe area to prevent unauthorized access. Dexamethasone should be stored at controlled room temperature, 68-77°F (20-25°C) and not frozen, and according to label requirements.

5.2.4 Handling

Dexamethasone should be handled by trained pharmacy staff. The use of gloves and other appropriate protective clothing is recommended as necessary.

5.2.5 Availability and ordering

Dexamethasone supply will be obtained through commercial supply. The investigator will order drug supply from commercial supply and will not be provided for the current trial.

5.2.6 Preparation

Dexamethasone is an oral drug, and does not require specific preparation details.

6.0 CRITERIA FOR SUBJECT ELIGIBILITY

6.1 Subject Inclusion Criteria

Patients fulfilling the following criteria will be eligible for entry into this study:

- Patients must be 18 years of age or above at the time of enrollment.
- Patients must show evidence of *asymptomatic* relapse and/or progression of disease (increasing M spike in serum or urine by consensus criteria) while on lenalidomide maintenance after HDM/ASCT as part of initial line of therapy. Patients who have not had an HDM/ASCT as part of initial line of therapy but who are on continuous/maintenance lenalidomide after initial therapy will be permitted on study.
- Patient must have myeloma that is measurable by either serum or urine evaluation of the monoclonal component or by assay of serum free light chains. Measurable disease is defined as one or more of the following: serum M-protein ≥ 0.5 g/dl, urine M-protein ≥ 200 mg/24 h, and/or serum FLC assay: involved FLC level > 10 mg/dL with abnormal serum FLC ratio.
- Patients must have adequate organ function including: Hepatic function with Bilirubin $< 2x$ the upper limit of normal and ALT and AST $< 3x$ the upper limit of normal; renal function with creatinine clearance ≥ 60 ml/min using the Cockcroft-Gault formula; hematologic function as defined by an absolute neutrophil count > 1000 neutrophils per microliter, platelet $> 50,000$ platelets per microliter and hemoglobin of ≥ 9 gm/dL without transfusion support.
- All study participants must be registered into the mandatory Revlimid REMS® program, and be willing and able to comply with the requirements of the REMS® program.
- Females of child bearing potential (FCBP)¹ must adhere to the scheduled pregnancy testing as required in the Revlimid REMS® program. FCBP must have a negative serum

¹ A female of childbearing potential is a sexually mature female who: 1) has not undergone a hysterectomy or bilateral oophorectomy; or 2) has not been naturally postmenopausal for at least 24 consecutive months (i.e., has had menses at any time in the preceding 24 consecutive months).

MEMORIAL SLOAN-KETTERING CANCER CENTER IRB PROTOCOL

IRB#: 11-107A(12)

or urine pregnancy test with a sensitivity of at least 50 mIU/mL within 10 – 14 days and again within 24 hours prior to prescribing lenalidomide for Cycle 1 (prescriptions must be filled within 7 days) and must either commit to continued abstinence from heterosexual intercourse or begin TWO acceptable methods of birth control, one highly effective method and one additional effective method AT THE SAME TIME, at least 28 days before she starts taking lenalidomide. FCBP must also agree to ongoing pregnancy testing. Men must agree to use a latex condom during sexual contact with a FCBP even if they have had a successful vasectomy. See Appendix: Risks of Fetal Exposure, Pregnancy Testing Guidelines and Acceptable Birth Control Methods.

6.2 Subject Exclusion Criteria

The following patients will be ineligible for registration onto this study:

- Patients with *symptomatic* relapse and/or progression of multiple myeloma. (Appendix A).
- Patients with plasma cell leukemia.
- Karnofsky performance score less than 70% or ECOG performance status greater than 2.
- Patients with uncontrolled bacterial, viral or fungal infections (currently taking medication and progression of clinical symptoms).
- Patients with prior malignancies except resected basal cell carcinoma or treated cervical carcinoma in situ or other cancer treated with curative intent > 5 years previously. Cancer treated with curative intent < 5 years previously will not be allowed unless approved by the Protocol Chairs.
- Female patients who are pregnant (positive β -HCG) or breastfeeding. (Lactating females must agree not to breast feed while taking lenalidomide).
- Patients seropositive for the human immunodeficiency virus (HIV).
- Prior organ transplant requiring immunosuppressive therapy.
- Patients who were previously exposed to higher doses of lenalidomide and who developed severe adverse events at higher doses that preclude incremental dosing.

7.0 RECRUITMENT PLAN

This study will be conducted at MSKCC and other collaborating medical centers that are members of the newly established Tri-State Transplant Consortium. It is anticipated that 15 patients will be enrolled from MSKCC and 38 patients will be enrolled from the collaborating centers. At MSKCC, patients will be recruited from the large population of patients who currently undergo (or have undergone) HDM/ASCT either on the currently accruing transplant clinical trial (IRB # 09-171), or past clinical trial (IRB # 05-080), which both include maintenance therapy with lenalidomide after HDM/ASCT as part of management; patients will also be recruited among patients who have been transplanted off protocol and receive maintenance lenalidomide after transplantation, a practice that has been gaining momentum in the past year. Patients who have not had an ASCT as part of initial line of therapy but are on continuous/maintenance lenalidomide will also be permitted on study. This trial will also be open at collaborating centers which have agreed to participate and we anticipate that a substantial proportion of patients will

MEMORIAL SLOAN-KETTERING CANCER CENTER IRB PROTOCOL

IRB#: 11-107A(12)

be accrued through this collaboration. All patients will be registered through MSKCC. All patients will be enrolled and followed by physicians at MSKCC and collaborating centers. All co-investigators agree to follow the treatment in the protocol and to conduct the proposed investigation according to recognized principles of good clinical practice. Participation is voluntary. Efforts will be made to ensure that women and minority groups are adequately represented in this trial. Each patient must be informed about the neoplastic nature of his/her disease and willingly consent to participating in this study. Every patient will be informed of the procedures to be followed, the potential benefits, side effects, risks, and discomforts of the trial and of potential therapeutic alternatives. All participants will be required to sign statements of informed consent and research authorization that conform to FDA, IRB and HIPAA guidelines. Informed consent will be documented by the use of a written consent form that has been approved by the MSKCC IRB.

Potential research subjects will be identified by a member of the patient's treatment team, the protocol investigator, or research team at Memorial Sloan-Kettering Cancer Center (MSKCC). If the investigator is a member of the treatment team, s/he will screen their patient's medical records for suitable research study participants and discuss the study and their potential for enrolling in the research study. Potential subjects contacted by their treating physician will be referred to the investigator/research staff of the study.

The principal investigator may also screen the medical records of patients with whom they do not have a treatment relationship for the limited purpose of identifying patients who would be eligible to enroll in the study and to record appropriate contact information in order to approach these patients regarding the possibility of enrolling in the study. This will allow the study team to keep track of all patients on lenalidomide maintenance therapy for multiple myeloma that may subsequently be eligible to enroll onto this study. The study staff and PI will review lists from Darwin queries. The patients on these queries will be tracked via a log.

During the initial conversation between the investigator/research staff and the patient, the patient may be asked to provide certain health information that is necessary to the recruitment and enrollment process. The investigator/research staff may also review portions of their medical records at MSKCC in order to further assess eligibility. They will use the information provided by the patient and/or medical record to confirm that the patient is eligible and to contact the patient regarding study enrollment. If the patient turns out to be ineligible for the research study, the research staff will destroy all information collected on the patient during the initial conversation and medical records review, except for any information that must be maintained for screening log purposes.

In most cases, the initial contact with the prospective subject will be conducted either by the treatment team, investigator or the research staff working in consultation with the treatment team. The recruitment process outlined presents no more than minimal risk to the privacy of the patients who are screened and minimal PHI will be maintained as part of a screening log. For these reasons, we seek a (partial) limited waiver of authorization for the purposes of (1) reviewing medical records to identify potential research subjects and obtain information relevant to the enrollment process; (2) conversing with patients regarding possible enrollment; (3)

MEMORIAL SLOAN-KETTERING CANCER CENTER
IRB PROTOCOL

IRB#: 11-107A(12)

handling of PHI contained within those records and provided by the potential subjects; and (4) maintaining information in a screening log of patients approached (if applicable).

This limited waiver will apply only to MSKCC. Any participating sites that require a limited waiver must obtain it from their own local IRB/Privacy Board (PB) via a separate protocol addendum or request. It is the responsibility of the MSKCC staff to confirm the participating data collection site(s) have a limited waiver approved by their local IRB(s)/PBs.

8.0 PRETREATMENT EVALUATION

The following tests will be done within 7 days prior to enrollment:

- Mandatory pregnancy test, serum or urine HCG (sensitivity of at least 50 mIU/mL) for FCBP.

Women are required to have 2 pregnancy tests prior initiation of lenalidomide as follows (Appendix B):

- The first is required within 10 to 14 days prior to prescribing lenalidomide
- The second within 24 hours of prescribing lenalidomide and prescription must be filled within 7 days.

The following tests will be done within 14 days prior to enrollment:

- History and physical exam including vital signs, height, weight, performance status, and toxicity assessment using CTCAE 4.0.
- Serum M-spike studies: Serum protein electrophoresis (SPEP), serum immunofixation (IF) and quantitative immunoglobulins, and serum free light chain assay
- Urine M-spike studies: Twenty-four hour urine for total volume and total protein (TV, TP), immunofixation (IF), protein electrophoresis (UPEP), N-telopeptides and creatinine clearance using the Cockcroft-Gault formula
- Comprehensive Metabolic Panel (includes Albumin, Alkaline Phosphatase, ALT, AST, BUN, Calcium, Carbon dioxide, Chloride, Creatinine, Glucose, Potassium, Sodium, Total Bilirubin, Total Protein), beta2-microglobulin, C-reactive protein, LDH
- CBC with differential
- INR/PTT, BNP, and troponin.
- Electrocardiogram (EKG)
- Mandatory pregnancy test, serum or urine HCG (sensitivity of at least 50 mIU/mL) for FCBP.

Women are required to have 2 pregnancy tests prior initiation of lenalidomide as follows

MEMORIAL SLOAN-KETTERING CANCER CENTER
IRB PROTOCOL

IRB#: 11-107A(12)

(Appendix B):

- o The first is required within 10 to 14 days prior to prescribing lenalidomide
- o The second within 24 hours of prescribing lenalidomide and prescription must be filled within 7 days.

The following tests will be performed within 56 days prior to patient enrollment:

- Hepatitis A, B, C serologies and HIV I/2 test
- A skeletal survey that should be reviewed at MSKCC or the participating site if not performed at MSKCC or the participating site. (Please note: the skeletal survey is not required if a PET scan has been completed)
- PET scan or total body MRI if available (optional)
- A routine bone marrow examination, including biopsy sample for H & E stain and immunohistochemical staining for CD 138, CD20, kappa and lambda light chains; bone marrow aspirate samples for Giemsa staining, flow-cytometry, cytogenetic analysis, and FISH analysis for chromosomes 1, 4, 11, 13, 14, 17 abnormalities

9.0 TREATMENT/INTERVENTION PLAN

9.1 Treatment Plan

- Lenalidomide dose will begin at 25 mg PO daily for 21 days of a 28-day-cycle adjusted for toxicity, if necessary. Once the dose of lenalidomide is reduced for toxicity, no dose-re- escalation is permitted.
- If a dose of lenalidomide is missed, it should be taken as soon as possible on the same day. If it is missed for the entire day, it should not be made up.
- Patients taking more than the prescribed dose of lenalidomide should be instructed to seek emergency medical care if needed and contact study staff immediately.
- Only one cycle of therapy may be dispensed to the patient each month. Lenalidomide capsules should be swallowed whole, and should not be broken, chewed or opened.
- Special Handling Instructions: Females of childbearing potential should not handle or administer lenalidomide unless they are wearing gloves.
- Record of administration: Accurate records will be kept in the source documents of all drug administration (including prescribing and dosing). Patients will be instructed to bring their complete medication diary (refer to Appendix D) to each study visit for assessment of compliance.

MEMORIAL SLOAN-KETTERING CANCER CENTER IRB PROTOCOL

IRB#: 11-107A(12)

- Patient will be evaluated for response and toxicity after every cycle and the response to lenalidomide intensification will be assessed after every cycle of therapy.
 - Patients with at least SD after 2 cycles of lenalidomide will continue on lenalidomide until asymptomatic POD at which time dexamethasone will be added at a dose of 40 mg PO weekly for the next cycle.
 - Patients with asymptomatic POD after 2 cycles of lenalidomide will have dexamethasone added to lenalidomide at a dose of 40 mg PO weekly with the next cycle.
 - Patients with further asymptomatic POD after any cycle of lenalidomide and dexamethasone will be taken off study and treated at the discretion of the treating physician. Note that further POD after the addition of dexamethasone will be determined compared to the new M spike baseline just prior to the addition of dexamethasone.
- Once patients are started on dexamethasone, they will also receive prophylaxis medication including Bactrim DS, one tablet PO TIW, fluconazole, 100 mg PO Daily, ASA 81 mg PO daily, and a PPI.
- Note that patients with symptomatic POD at any point in time during treatment will be taken off study.

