9.3 Supportive Care

- Monthly IV bisphosphonates (either Zometa or Pamidronate according to institutional preference) may be initiated or continued according to local institutional practice.
- Patients can receive filgrastim or pegylated filgrastim for an ANC < 109/L.
- Radiation therapy is not permitted concurrently in this trial.
- Transfusion thresholds for blood product support should be per institutional guidelines. All blood products will be irradiated.
- Treating physicians should be aware of the increased risk of DVT and PE with lenalidomide when combined with dexamethasone and have heightened vigilance regarding this possible toxicity. There is no clear evidence that the risk of DVT is increased on lenalidomide alone. Aspirin 325 mg/day orally should be administered during lenalidomide therapy when associated with dexamethasone unless the patient is treated with alternate prophylaxis of either low molecular weight heparin or Coumadin. This will be left to the discretion of the treating physician.
- Concurrent use of erythropoietin requires full anticoagulation of patients with therapeutic doses of LMWH or Coumadin. Anticoagulation should be held for platelet counts <50,000/mm³.
- Prophylaxis therapy should be added when patient start dexamethasone including fluconazole 100mg PO daily, Bactrim DS, three days a week, and a PPI daily.

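### Sections 9.1 and 9.3 give two different aspirin doses, 81 mg and 325 mg daily, for the same patients on lenalidomide plus dexamethasone

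*Combined protocol and SAP*

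**What the plan says.** Section 9.1 (Treatment Plan) sets out what happens when dexamethasone is added: "Once patients are started on dexamethasone, they will also receive prophylaxis medication including Bactrim DS", then fluconazole, then "ASA 81 mg PO daily, and a PPI". The instruction is mandatory in tone and has no exception.

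Section 9.3 (Supportive Care) covers the same situation. It first warns that "Treating physicians should be aware of the increased risk of DVT and PE with lenalidomide when combined with dexamethasone". It then says "Aspirin 325 mg/day orally should be administered during lenalidomide therapy when associated with dexamethasone", with one exception: "unless the patient is treated with alternate prophylaxis of either low molecular weight heparin or Coumadin". The bullet closes with "This will be left to the discretion of the treating physician".

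The last bullet of 9.3 returns to prophylaxis at the start of dexamethasone: "Prophylaxis therapy should be added when patient start dexamethasone including fluconazole 100mg PO daily, Bactrim DS, three days a week, and a PPI daily". Aspirin is not on that list.

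**The concern.** Both sections tell the site what aspirin to give to a patient on lenalidomide plus dexamethasone, and they give different doses. The protocol singles out this combination for thromboembolic risk. Bleeding is relevant too: section 11.1 lists low platelets among the likely effects of lenalidomide, and section 11.2 lists bleeding stomach ulcers as a rare but serious effect of dexamethasone. The aspirin dose is therefore a real clinical instruction.

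Section 7.0 expects 38 of the 53 patients from collaborating centers and 15 from the lead center. One site may follow 9.1 and another 9.3, and each could cite the protocol. The site audits described under Quality Assurance for Participating Sites check treatment against the protocol, and here the auditor would have two standards to choose from.

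What is at stake is patient safety and site compliance. Response is judged on myeloma criteria, and thromboembolic events enter the analysis only through descriptive toxicity reporting, so the primary test is not involved.

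**Working it through.** The plan has no figure to reproduce. The check is a comparison of text, followed by simple arithmetic on size.

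**1. Do the two instructions have the same trigger?** Yes. Section 9.1 applies once dexamethasone is started. Section 9.3 applies when lenalidomide is given with dexamethasone. Under sections 1.4, 4.2 and 9.1, dexamethasone enters the trial only as an addition to lenalidomide, so starting it meets both conditions.

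**2. The instructions side by side**

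| | 9.1 Treatment Plan | 9.3 Supportive Care |
|---|---|---|
| Aspirin dose | 81 mg daily | 325 mg daily |
| Strength of wording | will receive | should be administered |
| Exception for LMWH or Coumadin | none | yes |
| Physician discretion | none stated | stated at the end of the bullet |
| Fluconazole 100 mg daily, Bactrim DS three times a week, a PPI | listed | listed in the last bullet |

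The two sections agree on three of the four drugs. Aspirin is the one that differs.

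**3. Which patients are caught?**
- On neither anticoagulant: both doses apply, 81 mg and 325 mg.
- On LMWH or Coumadin: 9.3 exempts the patient from aspirin, whereas 9.1 read literally still adds 81 mg. This can arise by design, because 9.3 requires full anticoagulation with LMWH or Coumadin when erythropoietin is used.

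**4. Does any other text settle it?** No. No other section gives an aspirin dose or says which of the two prevails. The last bullet of 9.3 leaves aspirin out, so it neither confirms nor corrects either dose.

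**5. Size**
- Difference in dose: 325 − 81 = 244 mg daily; ratio 325/81 = 4.01.
- Patients affected: the documents give no expected share who will receive dexamethasone. Assumed shares of the 53 evaluable patients give:
  - 25%: 0.25 × 53 = 13.25
  - 50%: 0.50 × 53 = 26.5
  - 75%: 0.75 × 53 = 39.75

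That is about 13 to 40 patients, before removing those on LMWH or Coumadin, for whom the documents give no number. The documents also give no clot or bleeding rate by aspirin dose, so no difference in events can be worked out.

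**The case against.** The strongest reply is the discretion sentence in 9.3. Its wording is not expressly limited to the choice of agent. Read broadly, it makes 325 mg advisory, and a physician who gives 81 mg complies with both sections. That path is arguable, and it makes the conflict less than absolute. It does not remove it. The sentence comes straight after the choice between aspirin and an anticoagulant, so choice of agent is the more natural reading. It names no other aspirin dose and does not refer to 9.1. Section 9.1 allows no discretion, so even on the broad reading a physician who gives 325 mg departs from 9.1.

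A second reply is that varied thromboprophylaxis is already part of the plan, since aspirin, LMWH and Coumadin are all allowed. That is true, and it weakens any argument that sites should be uniform. But the permitted variation is between agents. Two fixed doses of one agent, each stated as the instruction, is a different matter.

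Third, no harm is shown: neither section leaves these patients without prophylaxis, and the physician is told to watch for clots. This stands, and it limits the weight of the point. Likewise, the range of 13 to 40 patients rests on an assumed share and only illustrates scale. The omission of aspirin from the last bullet of 9.3 may simply avoid repetition. It is not further evidence of conflict, only a place where the dose could have been settled and was not.

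**Conclusion.** The concern holds. For patients on lenalidomide plus dexamethasone without LMWH or Coumadin, the protocol states two aspirin doses that differ by 244 mg daily, about four-fold, and does not say which applies. For patients who are on one of those anticoagulants, 9.1 lacks the exception that 9.3 grants. The discretion sentence softens the first problem without resolving it, and does not reach the second.

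That the two instructions differ is certain from the text. The number of patients is not: about 13 to 40 of 53 depends on an assumed dexamethasone share of 25% to 75% and is an upper figure at each share. Nothing here shows which dose is right, and no effect on clot or bleeding rates is claimed. Sample size, endpoint and the rule of 12 responders in 53 are untouched. The point should be corrected as a contradictory safety instruction. It is not a threat to the trial's conclusion.

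**What to change.** Have the clinical team choose one aspirin dose and state it in both the 9.1 prophylaxis bullet and the 9.3 aspirin bullet. In the same edit, copy 9.3's exception for patients on LMWH or Coumadin into 9.1, so that the two sections read alike. Notify all sites.

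The drafting cost is two bullets and a site notice, with no change to sample size, endpoints or analysis. The administrative cost is the amendment route in section 16.3.1: agreement of the principal investigator, review by the study supporter and approval by the lead center's IRB. If the amendment is not expedited, it also needs approval by each participating site's IRB within 90 days. Under that section, an amendment that results from a safety issue stops new enrollment at a site until its IRB approves, so how the change is classified should be settled with the lead center's IRB beforehand. Combining it with the next planned amendment would spare a separate round of submissions, and a clarifying notice could be considered in the meantime.
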